| GLP-2 | Glucagon-like peptide 2 |
| IB | Investigator’s Brochure |
| IBD | Inflammatory bowel disease |
| ICF | Informed Consent Form |
| ICH | International Conference on Harmonisation |
| IEC | Independent Ethics Committee |
| IRB | Institutional Review Board |
| IV | Intravenous |
| ITT | Intent-to-treat |
| MedDRA | Medical Dictionary for Regulatory Activities |
| MS | Mass spectrometry |
| NOAEL | No Observed Adverse Effect Level |
| PD | Pharmacodynamic |
| PK | Pharmacokinetic |
| PN | Parenteral nutrition |
| QD | Once daily |
| SAE | Serious adverse event |
| SAP | Statistical Analysis Plan |

| | |
|--------------------|--|
| SBS | Short bowel syndrome |
| SC | Subcutaneous |
| SMT | Safety Management Team |
| SOT | Start of Treatment |
| SUSAR | Suspected, unexpected, serious, adverse reaction |
| $t_{1/2\lambda z}$ | Terminal phase half-life |
| t_{max} | Time to maximum plasma concentration |
| ULN | Upper limit of normal |
| $V_{\lambda z}/F$ | Apparent volume of distribution |
| WHODD | World Health Organization Drug Dictionary |
| WMA | World Medical Association |

1 INTRODUCTION AND BACKGROUND INFORMATION

2.1 Study Design

This is an open-label, multicenter, 4-stage study consisting of an optimization/stabilization period (Stage 1), a 24-week treatment period in which all subjects will receive teduglutide 0.05 mg/kg/day (Stage 2), and a long-term extension (Stages 3 and 4).

At least 5 subjects may be enrolled during the recruitment period, which ends approximately 6 months after the initiation of the study.

Main Treatment Period (Stages 1 and 2)

Stage 1 will include a screening visit; a maximum 8-week PN/I.V. optimization period (if required); and a stabilization period that demonstrates stable PN/I.V. support for a minimum of 4 weeks to a maximum of 8 weeks.

If at screening a subject does not have a stable PN/I.V. volume, defined as a 48-hour urine output within 2 to 4 L, he/she will enter the optimization period, during which the minimally tolerated stable PN/I.V. volume will be determined during a period of up to 8 weeks. If it is not possible to keep the subject adequately hydrated and nourished within the target urine output range, the minimally tolerated PN/I.V. volume will be documented.

All subjects will then enter the stabilization period, during which the target volume will be maintained for at least 4 consecutive weeks (8 weeks maximum) prior to entering the dosing period (Stage 2).

If a subject fails to maintain a stable PN/I.V. volume for at least 4 consecutive weeks, the subject may start the optimization period again, beginning with Week 2 (Visit 1.1). Those subjects who fail to stabilize after 2 attempts will not proceed further and will not be included in Stage 2.

Stage 2 will be a 24-week dosing period, during which subjects will self-administer teduglutide 0.05 mg/kg/day at home. Stage 2 will begin with baseline assessments of hydration and nutritional status once the subjects have demonstrated PN/I.V. stability for 4 to 8 weeks. At least 5 subjects will be enrolled. The on-treatment study visits will occur at Weeks 2, 4, 8, 12, 16 and 20, with the last scheduled visit at Week 24 of Stage 2.

Extension Treatment Period (Stages 3 and 4)

[figure not shown]
Stages 3 and 4 constitute the long-term extension portion of the study. Stage 3, which will begin immediately following Stage 2, will include subjects who complete the main treatment period and who are willing to continue with treatment teduglutide 0.05 mg/kg/day SC for up to an additional 24 months. In Stage 4, which will begin immediately following Stage 3, subjects will continue treatment with teduglutide 0.05 mg/kg/day SC in Study TED-C14-004 until teduglutide is commercially available for each subject, the subject's participation in this study is discontinued, or the study is discontinued.

Any subject who achieves complete independence from PN/I.V. support at any time during the Stages 2, 3 or 4 treatment periods will continue to receive teduglutide treatment. If a subject relapses following achievement of PN/I.V. independence, PN/I.V. support will be re-initiated and the subject will continue receiving teduglutide.

A schematic representation of the study design is displayed in [Figure 1](#).

The Schedule of Evaluations and Procedures for each stage are outlined in Section 6.4 of the protocol.

Figure 1 Study Diagram

2.2 Objective

The objectives of this clinical study are to evaluate the safety, efficacy and pharmacokinetics of teduglutide in Japanese subjects with PN/I.V.-dependent SBS over a 24-week period (Stage 2) followed by a long-term extension (Stages 3 and 4) to evaluate safety and continued efficacy.

2.2.1 Efficacy and Pharmacodynamic Endpoints - Stage 2

The efficacy endpoints are as follows:

- Absolute and percent change from baseline in weekly PN/I.V. volume over 24 weeks (by visits and at end of treatment [EOT]). Weekly PN/I.V. volume will be based on the subject diary recordings.
- Percentage of subjects who demonstrate a response at Week 20 and again at Week 24. A response is defined as the achievement of at least a 20% reduction from baseline (Visit 2) in weekly PN/I.V. volume.
- Change in days per week of PN/I.V. support
- Changes in plasma citrulline levels from baseline to Week 24 (or EOT)

2.2.2 Efficacy and Pharmacodynamic Endpoints – Stages 3 and 4

For Stages 3 and 4, absolute and percent change from baseline in weekly PN/I.V. volume and changes in days per week of PN/I.V. support and plasma citrulline levels will continue to be evaluated throughout the long-term extension.

2.2.3 Pharmacokinetic Endpoints – Stage 2 Only

Pharmacokinetic Endpoints are described and analyzed in the interim report.

2.2.4 Safety Objectives

The safety and tolerability of teduglutide treatment will be assessed by evaluation of adverse events (AEs); 12-lead electrocardiogram (ECG); vital signs; laboratory safety data; antibodies to teduglutide and to *Escherichia coli* protein (ECP) and changes in 48-hour urine output, body weight and body mass index (BMI). An abdominal ultrasound and colonoscopy/sigmoidoscopy of remnant colon will be done during the stabilization period if these procedures were not performed during the 6 months prior to screening. Colonoscopy/sigmoidoscopy will be repeated at the end of the main treatment period

(Stage 2) and at the end of the extension treatment period (Stage 3 and 4). For all subjects with a history of Crohn's disease, an upper GI contrast series with small bowel follow-through will be performed during the stabilization period, prior to the baseline visit.

2 DETERMINATION OF SAMPLE SIZE

The sample size is determined based on the small patient population and the feasibility of the study, rather than power calculation.

3 UNBLINDING PROCEDURES

No unblinding procedures apply as this is an open-label study.

4 DATA MANAGEMENT

Clinical data are collected using eCRF and data are processed by a clinical research organization (CRO).

Details about data management, including the eCRF design, the EDC system, data validation and discrepancy management, reconciliation of data from different sources, and electronic data transfer, are included in the Data Management Plan for this study.

5 STATISTICAL/ANALYTICAL ISSUES

6.1 General Methodology

All statistical procedures will be completed using SAS version 9.2 or later.

The small sample size resulting from the small study population requires the use of descriptive statistics with a goal of summarizing the sample and thus discourages the use of inferential statistics. Continuous variables, including those assessed on a discrete scale, will be summarized using descriptive statistics including number of subjects, mean, median, standard deviation, maximum, and minimum. For categorical variables, statistical summaries will include number of subjects and percentages.

For summary purposes, the baseline value will be defined as the last available pre-dose value. Scheduled visits will be summarized as provided in the electronic case report forms (eCRFs). An End of Treatment (EOT) time point, defined as the last determination of endpoint or last available measurement from the date of first dose, will be analyzed in addition to the scheduled visits.

Study Day will be calculated as the date of the evaluation minus the date of the first day of study medication for study days before the first day of study medication, and the date of the evaluation minus the date of the first day of study medication plus one otherwise.

All summaries will be presented by one group, unless otherwise specified. Subjects in the eCRF database who were not treated with study medication will be included in the disposition table as “Enrolled”. For subject data listings, these subjects will be listed in a treatment group specified as ‘Not Treated’.

6.2 Adjustments for Covariates/Prognostic Variables

No adjustments for covariates are planned in the statistical analyses.

6.3 Handling of Dropouts or Missing Data

All subjects in the analysis population defined in Sections 7.1, 7.2 and 7.3 will be included in the associated analyses.

Missing safety parameters will not be imputed.

Details on how to handle partial dates for adverse events and prior/concomitant medications will be discussed under Safety Evaluation.

6.4 Interim Analyses and Data Monitoring

There was one interim analysis of study. A final analysis of study data will be done at the end of the study.

6.5 Multicenter Studies

Because a small number of subjects are expected at each center, data from all centers will be pooled (i.e., no center effect will be included in statistical models).

6.6 Multiple Comparisons/Multiplicity

As there will be no statistical testing given the small sample size, no adjustment for multiple comparisons will be made.

6.7 Active-Control Studies Intended to Show Equivalence

This study was not an active control study intended to show equivalence.

6.8 Examination of Subgroups

No subgroup analyses will be conducted give the small number of patients in this study.

6 ANALYSIS POPULATIONS AND VISITS

7.1 Efficacy/PD Analysis Populations

The intention-to-treat (ITT) population will consist of all subjects who are enrolled and eligible to enter Stage 2. The ITT population will be the primary analysis population analyzed for efficacy/PD endpoints.

The Per Protocol population will consist of all subjects in the ITT population who completed Stage 2 without any major protocol violations that could potentially affect the efficacy conclusions of the study. The major protocol violations will be determined with the following conditions, but not limited to:

1. Subjects with no detectable TED level in blood as part of PK assessment or no PK assessment.
2. Absence of Week 20 and Week 24 visits
3. Non-compliance to study medication for the treatment group

Compliance is defined in Section 9.
4. Discrepancies between planned and actual treatment

The Per Protocol (PP) population will be the secondary analysis population analyzed for efficacy endpoints.

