9 MEASUREMENTS OF TREATMENT COMPLIANCE

Percent compliance will be calculated as 100 times the doses administered divided by the number of days on treatment. Doses administered will be calculated as the total number of vials dispensed minus the total number of vials returned unused during the study period. Number of days on treatment is calculated as (last dose date – first dose date +1). Drug accountability information, first dose date, last dose date, and study medication interruptions are reported in the eCRF. Subjects will be considered compliant overall for study medication if the calculated compliance is $\geq 80\%$. Overall treatment compliance will be presented for both percent compliance calculations using descriptive statistics and the number and percentage of subjects who are $\geq 80\%$ compliant for both the ITT and Safety Populations. Treatment compliance by visit will not be calculated. Compliance for Stage 2 Only will also be calculated.

Information about interruptions of study medication (start date of interruption, date study medication resumed, and reason for interruption) is included in data listings.

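### Two Per Protocol conditions in SAP Section 7.1 do not work as written: the visit rule literally needs both visits missed, and the compliance rule leads only to a whole-treatment cut-off

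*SAP*

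**What the plan says.** SAP Section 7.1 defines the set as follows: "The Per Protocol population will consist of all subjects in the ITT population who completed Stage 2 without any major protocol violations" that might affect the efficacy conclusions. It then introduces four conditions with the words "The major protocol violations will be determined with the following conditions, but not limited to". The second is "Absence of Week 20 and Week 24 visits". The third is non-compliance with study medication, for which the text says "Compliance is defined in Section 9". The set is named as the secondary population for efficacy.

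Section 2.1 lists the Stage 2 visits, "with the last scheduled visit at Week 24 of Stage 2". Sections 2.2.1 and 11.1 define the main response endpoint as a reduction of at least 20% in weekly PN/I.V. volume at Week 20 and again at Week 24.

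Section 9 sets out the compliance calculation. For the numerator, "Doses administered will be calculated as the total number of vials dispensed minus the total number of vials returned unused during the study period". The denominator is the number of days from first to last dose, both included. For the cut-off, "Subjects will be considered compliant overall for study medication if the calculated compliance is" at least 80%. The section adds that a Stage 2 figure will be calculated too, and Table 14.1.10.1.1 is listed for it. It gives that figure no cut-off and does not connect it to PP.

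**The concern.** A PP set should keep the subjects whose Stage 2 course allows the Stage 2 endpoints to be judged. Two of the four conditions do not clearly do this.

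The visit condition repeats, almost entirely, what completion of Stage 2 already demands. The case that matters for the two-visit response, one visit missed and the other attended, passes through it.

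The compliance condition leads to a cut-off on the whole treatment period. Stage 3 lasts up to 24 months and Stage 4 has no fixed end, so the extension can outweigh the 24 weeks of Stage 2. A subject under-dosed in Stage 2 could be kept, and a subject fully dosed in Stage 2 could be removed for later behaviour. Membership would also depend on how long each subject stayed in the extension.

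At stake are the seven PP efficacy tables (14.2.1.2, 14.2.1.4, 14.2.2.2, 14.2.2.4, 14.2.3.2, 14.2.3.4 and 14.2.4.2).

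**Working it through.** The SAP gives no figure of its own to reproduce here. Two checks were made.

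**Visit condition.** The four attendance patterns:

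| Week 20 | Week 24 | Excluded if both must be absent | Excluded if either is absent | Response at both visits can be confirmed |
|---|---|---|---|---|
| yes | yes | no | no | yes |
| yes | no | no | yes | no |
| no | yes | no | yes | no |
| no | no | yes | yes | no |

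The literal reading removes one of the three patterns in which the two-visit response cannot be confirmed. That pattern is the one least likely in a subject "who completed Stage 2 without any major protocol violations".

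**Compliance condition.** Inputs:
- Stage 2 days: 24 × 7 = 168 (Section 2.1).
- Cut-off: 80% of days from first to last dose (Section 9).
- Extension days E: assumed 183, 365 and 730 for 6, 12 and 24 months. Twenty-four months is the Stage 3 maximum. Stage 4 could add more.
- Total days: T = 168 + E.

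The lowest Stage 2 compliance that still passes, with every extension dose taken, is (0.8T − E)/168, floored at zero. The extension compliance below which a subject with 100% in Stage 2 fails is (0.8T − 168)/E.

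| Extension | T | 0.8T | Lowest passing Stage 2 compliance | Extension compliance below which 100% in Stage 2 fails |
|---|---|---|---|---|
| 6 months | 351 | 280.8 | (280.8 − 183)/168 = 58.2% | (280.8 − 168)/183 = 61.6% |
| 12 months | 533 | 426.4 | (426.4 − 365)/168 = 36.5% | (426.4 − 168)/365 = 70.8% |
| 24 months | 898 | 718.4 | (718.4 − 730)/168 < 0, so 0% | (718.4 − 168)/730 = 75.4% |

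The 0% entry is an arithmetical limit (730/898 = 81.3%). A first dose is needed to start the day count, and the separate condition on detectable drug in blood could remove an extreme case.

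Two less extreme cases, both assumed, with a 24-month extension:
- 60% in Stage 2, then 95%: (0.60 × 168 + 0.95 × 730)/898 = 794.3/898 = 88.5%, kept.
- 95% in Stage 2, then 70%: (0.95 × 168 + 0.70 × 730)/898 = 670.6/898 = 74.7%, removed.

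If the same cut-off is applied to Stage 2 alone, 0.8 × 168 = 134.4. At least 135 doses are then needed, whatever the length of the extension.

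**Weight of one subject.** In a set of five, each subject is 1/5 = 20 points. Removing one can move a response percentage by up to that much, for example from 4/5 = 80% to 4/4 = 100%.

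**The case against.** A reader might infer that the SAP fixes whole-study compliance as the PP test. It does not. Section 7.1 refers to Section 9 without naming a period, and Section 9 provides both an overall and a Stage 2 figure. It remains true that the only cut-off in Section 9 is attached to the overall figure, so a programmer following the reference arrives there.

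A reader might also infer that the visit condition can never be met. That is too strong, because the SAP does not define completion of Stage 2. The wording can be taken to mean absence of either visit, and the list of violations is open, so a subject missing only Week 20 could still be excluded by judgement. These points make the rule ambiguous rather than empty. In an open-label study, however, a case-by-case exclusion would be made with outcomes visible.

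A subject missing only Week 20 is not non-evaluable in general. Change in volume at Week 24, response by visit and days of support can still be observed. The two-visit response is also settled as a failure if the visit attended shows no response.

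The PP by-visit tables are not restricted to Stage 2, so overall compliance has some relevance to what they show. This stands, and is a cost of the change proposed below.

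Finally, a reader might infer that the vial-count formula is wrong because lost vials count as doses. The formula is clearly stated and contradicts nothing else in the SAP. Administration, accountability and interruptions are all listed (Listings 16.2.5.1 to 16.2.5.3), and the documents give no rate of loss.

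**Conclusion.** The concern holds for both conditions, as defects of wording. Taken literally, the visit condition would hardly ever exclude a Stage 2 completer, and it keeps a subject missing only Week 20. The compliance condition leaves the period unnamed and leads to the overall cut-off. On that reading, misclassification is possible in both directions, within the limits tabulated above.

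Those limits rest on 168 Stage 2 days and on assumed extension lengths. The lower limits also assume full extension dosing, and the upper ones full Stage 2 dosing. They show what the rule permits, not what is expected to happen.

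The impact is limited: PP is secondary to ITT, and the analyses are descriptive with no testing. It is not negligible, because enrolment may be as small as five. Five is the stated minimum enrolment, not a known size of the PP set.

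**What to change.** In Section 7.1:
- Change condition 2 to absence of the Week 20 visit or the Week 24 visit.
- Change condition 3 to Stage 2 compliance below 80%, citing the Stage 2 calculation already planned for Table 14.1.10.1.1.

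Condition 2 should not also require an evaluable diary interval. That would drop subjects from the PP tables based on investigator-prescribed data, which do not depend on the diary.

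The cost is two lines of SAP text and no new data. PP may lose a subject whose other endpoints are observable; that subject remains in the ITT tables. PP summaries at Stage 3 and Stage 4 visits would no longer screen on extension compliance, and a table footnote can say so.

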7.2 Safety Analysis Population

The Safety Population will consist of all subjects in the ITT population who receive at least one dose of study medication. All safety analyses will be conducted on this population, unless otherwise specified.

All data will be included in the listings.

7.3 PK Analysis Population (Stage 2 Only)

The PK Analysis Population is defined as all subjects, at Stage 2, in the Safety Analysis Population for whom the primary PK data are considered sufficient and interpretable.

7.4 Windowing Visits

Although there is a visit window from 2 to 7 days around the expected visit date, nominal visits will be used for the per-visit analyses. Therefore, no windowing of visits by actual study day will be done for data obtained at the scheduled visits. For subjects who withdraw from the study pre-maturely, if the early termination visit falls into the window of a scheduled visit as defined in the protocol, the early termination visit is also summarized for that scheduled visit, unless the scheduled visit already took place.

7 STUDY SUBJECTS

8.1 Subjects Screened and Enrolled

The number of subjects enrolled, and the number of subjects treated will be presented.

8.2 Study Analysis Populations

The number and percent of subjects in each study analysis population (i.e., ITT and Safety) will be presented.

8.3 Protocol Deviations

A listing of subjects with protocol deviations will be presented in the data listings. The number and percent of subjects with protocol deviations will be summarized. The unique type of protocol deviations will be summarized for the ITT population.

8.4 Disposition of Subjects

For the ITT and Safety populations, study enrollment and completion will be summarized by the number and percent of subjects who complete Stages 2, Stage 3, Stage 3 V7 and Stage 4. The number and percent of subjects by the reason for discontinuing each stage early will also be presented.

8 DEMOGRAPHIC AND OTHER BASELINE CHARACTERISTICS

9.1 Analysis of Demographic and Other Baseline Characteristics

The baseline and demographic characteristics will be summarized with descriptive statistics defined in Section 6.1 for the ITT and Safety Population. Demographic and baseline characteristics to be presented include:

- age (at informed consent date) in years, both as a continuous parameter and by categories of <45, 45-<65, and ≥ 65 .

- gender
- race
- ethnicity
- height (cm) at the Baseline visit
- weight (kg) at the Baseline visit
- body mass index (BMI) (kg/m^2) at the Baseline visit

BMI is calculated as body weight (kg)/body height² (m).

The following Short Bowel Syndrome History information collected at the Screening visit (i.e., Visit 1.0) will be summarized with descriptive statistics defined in Section 6.1 for the ITT and Safety Populations:

- Duration of SBS (years)
- reason for major intestinal resection (Crohn's disease, vascular disease, injury, volvulus, cancer, and other)
- stoma (Y/N), stoma type (jejunostomy, ileostomy, colostomy, other)
- Remaining colon (Y/N), estimated percent colon remaining, and colon in continuity (Y/N)
- Colonoscopy in the last 6 months (Y/N/NA)
- Total estimated remaining small intestinal length (cm) and category (< 25 cm, ≥ 25 cm; < 40 cm, ≥ 40 cm; < 60 cm, ≥ 60 cm)
- Distal/terminal ileum (Y/N) and ileocecal valve (Y/N)
- Method to determine remaining anatomy length (surgery, radiology, other)

Duration of SBS will be calculated as (Date of Informed Consent Form Signed – Date of Diagnosis of SBS +1)/365.25.

The following Parenteral Nutrition History information collected at the Screening visit (i.e., Visit 1.0) will be summarized with descriptive statistics defined in Section 6.1 for the ITT and Safety Populations:

- years since start of PN dependency
- prescribed weekly PN/IV volume
- actual weekly PN/IV volume
- prescribed weekly PN calorie
- actual weekly PN calorie
- prescribed weekly number of days of PN/IV
- actual weekly number of days of PN/IV

The following Crohn's Disease Evaluation information collected at the Screening visit (i.e., Visit 1.0) will be summarized with descriptive statistics defined in Section 6.1 for the ITT and Safety Population:

- Has a medical history of Crohn's disease (Y/N), and current clinical status of Crohn's disease (Active, Inactive)

The following Gastrointestinal-specific Testing information collected during the stabilization period will be summarized with descriptive statistics defined in Section 6.1 for the ITT and Safety Population:

- For subjects with Crohn's disease, upper gastrointestinal contrast series with small bowel follow-through (normal, abnormal not clinically significant, abnormal clinically significant)
- abdominal ultrasound (normal, abnormal not clinically significant, abnormal clinically significant)
- colonoscopy (normal, abnormal not clinically significant, abnormal clinically significant)
- sigmoidoscopy (normal, abnormal not clinically significant, abnormal clinically significant)

Colonoscopy and sigmoidoscopy will also be collected at the end of Stage 2 and Stage 3.

Partial dates for the start date of PN dependency and date of last surgical resection will use the first day of the month if only the day is missing. If both the day and month are missing, the first of January will be used.

Medical and surgical history will be coded using the Medical Dictionary for Regulatory Activities. Investigator verbatim as well as preferred terms and body systems will be included in the listings. The medical history will be summarized by system organ class (SOC) and preferred term (PT) within system organ class for the Safety Population, with SOC sorted alphabetically and PT within SOC by descending incidence.

